**TISCHMS-MSCNP-002
CLINICAL STUDY PROTOCOL**

NCT03355365

CLINICAL PROTOCOL: Summary Information

| | |
|--|--|
| TITLE | Autologous, Bone Marrow-Derived Mesenchymal Stem Cell-Derived Neural Progenitor Cells (MSC-NP), Expanded Ex Vivo; Administered Intrathecally |
| SPONSOR | Tisch MS Research Center of New York (Tisch MSRCNY) [name] [contact] |
| PROTOCOL NUMBER | TISCHMS-MSCNP-002 |
| VERSION NUMBER AND DATE | V8 08/26/2021 |
| PHASE OF CLINICAL INVESTIGATION | Phase II |
| IND NUMBER | 13889 |
| PRINCIPAL INVESTIGATOR | [name], FAAN Director and Chief Research Scientist Tisch MS Research Center of New York |
| NUMBER OF SITES | 1 |
| STUDY DESIGN | Phase 2, Double-Blind, Placebo-Controlled, randomized, Parallel Study of Intrathecal autologous MSC-NP Cells in Patients With MS |
| PRIMARY OBJECTIVE | To determine efficacy of multiple (6) intrathecal administrations of autologous MSC-NPs compared to placebo through assessment of disability outcomes |
| SECONDARY OBJECTIVES | To determine continued safety and tolerability of multiple intrathecal injections of MSC-NPs in patients with MS |
| NUMBER OF SUBJECTS | 50 |
| SUBJECT SELECTION CRITERIA | Inclusion Criteria (summary): SPMS or PPMS patients who have significant disability (EDSS between 3.0 and 6.5) that was not acquired within the last 12 months. Exclusion Criteria (summary): EDSS > 6.5, or anyone with comorbidities (past or present) that would put them at a higher risk for safety complications. |
| INVESTIGATIONAL NEW DRUG / INTENDED USE | Bone Marrow-Derived Mesenchymal Stem Cell-Neural Progenitor Cells (MSC-NP) for use as treatment for multiple sclerosis |
| CONTROL GROUP OR OTHER STUDY ARMS (if applicable) | Placebo (LP procedure) |
| DURATION OF SUBJECT | Subjects will participate in the study for 3 years |

| | |
|--|---|
| PARTICIPATION AND DURATION OF STUDY | 
 • Pretreatment screening and bone marrow aspiration: potentially up to 4 months • Treatment phase: 2 years, total 12 treatments (6 MSC-NP injections, 6 placebo lumbar punctures) every 2 months • Follow-up: 1 year |
| PRIMARY ENDPOINT | EDSS Plus (measured at baseline, month 6, month 13, month 20, month 27, and month 36) |
| SECONDARY ENDPOINTS | 
MSFC EDSS T25FW (timed 25 foot walk) 9HPT (9 hole peg test) 12-item MS Walking Scale urodynamic studies 6 Minute Walk Test Time to Progression (measured at month 13, month 27, and month 36) Progression on MRI (measured by percent change from baseline in total volume of T2 Lesions and percent change in total brain volume from baseline at month 13, month 27, and month 36)
 |
| SAFETY EVALUATIONS | 
Incidence of serious adverse events Incidence of minor adverse events (headache pain scale, fever) Brain, cervical, and thoracic MRI
 |

Principal Investigator: **[name], FAAN**
Tisch MS Research Center
[name]
[name]
[contact]
[contact]
Email: [contact]

Sub-Investigators (TMSRCNY): [name]
Tisch MS Research Center of New York
[name]
[name]
[contact]
[contact]
Email: [contact]

[name]
Tisch MS Research Center of New York

[name]
[name]
[contact]
[contact]
Email: [contact]

[name]
Tisch MS Research Center of New York
[name]
[name]
[contact]
[contact]
Email: [contact]

[name]
St. Luke's-Roosevelt Hospital Center
Hematology-Oncology
[name]
[name]
[contact]
[contact]
Email: [contact]

[name]
[name]
[name]
[contact]
[contact]
Email: [name]

[name]
Department of Healthcare Policy and Research
Weill Cornell Medical College
[name]
[name]
[contact]
[contact]
Email: [contact]

[name], MS
Department of Healthcare Policy and Research
Weill Cornell Medical College
[name]
[name]
[contact]

[contact]
[contact]

TMSRCNY Study Nurse(s): [name]
[name]

TMSRCNY Clinical Trial Manager: [name], BA

TMSRCNY Study Coordinators: [name], BA
[name], BA

Study Locations: Tisch MS Research Center of New York
(Treatment and Assessment site)

Clinical Protocol

1. Introduction:

1.1 Background:

Multiple sclerosis (MS) is an autoimmune-mediated chronic demyelinating disorder, and is the leading cause of disability in young adults after trauma. At present, there is no treatment that reverses the effects of established disease. Over the last 15 years, the outlook for newly diagnosed patients with MS has improved considerably because of therapeutic advances that ameliorate the aberrant immune responses seen in these patients. However, there are extremely limited treatments available for progressive MS, where progressive disease worsening and disability are associated with neurodegenerative mechanisms.

In attempting to develop a stem cell-based reparative therapy for MS we are investigating the use of autologous **MSC-derived neural progenitors (MSC-NPs)** administered in multiple intrathecal doses. The objective of this novel cellular therapy is to promote CNS repair and regeneration in patients with progressive MS, with the ultimate goal of reversal of disability.

1.2 Rationale:

MSC-NPs represent a neural subpopulation of MSCs from bone marrow with reduced pluripotency and minimized risk of ectopic differentiation, thus are likely to be more suitable for CNS delivery [1, 2]. Importantly, characterization of MSC-NPs demonstrated their immunoregulatory and trophic properties, and MSC-NPs derived from MS and non-MS patients alike were therapeutically viable [1]. In *in vitro* studies, the release of trophic growth factors, including hepatocyte growth factor (HGF), promoted the differentiation of myelin-forming oligodendrocytes, suggesting a possible mechanism of repair for MS. MSC-NPs also secrete abundant immunoregulatory cytokines, including TGF-beta and IL-6, that may suppress immune responses related to MS.

In preclinical studies, intrathecal (IT) MSC-NP treatment in EAE, the mouse model of MS, resulted in significantly improved neurological function [2]. Importantly, MSC-NPs were injected into mice with established chronic EAE [2], since progressive MS patients in need of regenerative therapies have long passed the phase of disease onset and are well into the neurodegenerative phase of the disease. These experiments were designed to mimic most closely the clinical trial design in humans, and included the following parameters: 1) Cells were injected intrathecally in mice rather than intravenously in order to best target damaged CNS tissue, 2) Cells were injected during the chronic phase of

EAE rather than the inflammatory phase, 3) Dose range from 2×10^4 to 1×10^6 cells was tested to inform dosing in human trials, and 4) Single vs. multiple dosing was tested to inform dosing regimen in human trials. We found that three injections of MSC-NPs spaced one week apart resulted in decreased cumulative EAE disease score in mice compared to single injections. Histopathological analysis on animals carried out 8 weeks after the third injection showed evidence of MSC-NP engraftment in the CNS. Neurological recovery was associated with increased spinal cord myelination, decreased immune infiltration in the CNS, and increased recruitment of endogenous progenitor cells. The multiple injection dosing regimen was well tolerated in mice.

In a pilot feasibility study, 6 MS patients with advanced disease were treated with 2-5 injections of escalating doses of autologous MSC-NPs administered intrathecally [3]. Patients were followed for an average of 7.4 years after initial injection. There were no safety concerns noted and no serious adverse events supporting both short-term and long-term safety of this experimental approach. Importantly, the data showed that multiple (up to 5) treatments were well tolerated. Incidentally, four of the six patients showed a measurable clinical improvement following MSC-NP treatment, providing further justification for phase I/II clinical trials.

Based on these pre-clinical and early clinical data supporting safety and efficacy, we are conducting an FDA-approved Phase I clinical trial to test safety and tolerability of 3 separate doses of up to 10 million MSC-NPs administered intrathecally with doses spaced 3 months apart [4]. Twenty subjects with progressive MS were enrolled. Inclusion criteria included those with established disability (EDSS 3.5 to 8.0) and stable disability (no progression 6-12 months prior to enrollment). All 20 patients received the 3 MSC-NP treatments spaced 3 months apart with 3 month follow-up assessments. The dosing regimen was found to be well tolerated, with only minor adverse events including transient headache (lasting only up to 48 hours post-treatment) and less commonly a transient fever (less than 100°F; always over within 24 hours). There were no safety concerns associated with the treatment. Efficacy trends show that 15 of the 20 patients have improved in at least one of the following categories: ≥ 0.5 improvement in EDSS; at least 20% improvement in 25 feet timed walk, greater than 20% positive change in none hole PEG test, moderate to marked improvement in muscle strength, or symptomatic and/or urodynamic improvement in bladder function. These results are remarkable because such reversal of disability in long standing SPMS and PPMS has not previously been reported.

Based on our phase I trial results that establish safety and tolerability and suggest efficacy, we have designed a phase II study with the primary goal of establishing efficacy. We propose to use the intrathecal (IT) route of injection of administration. This is because the IT route in our phase I study has proved safe, tolerable and given positive results and it has not been established that these

cells given by other routes such as IV is effective. In our clinical studies to date, doses of up to 10 million MSC-NPs are well tolerated [3, 4], therefore we propose to continue the same dosage for this phase II study.

The dosing regimen of the Phase II trial will consist of 6 separate intrathecal doses, spaced 2 months apart. This extended dosing is designed to achieve optimal results based on the dosing experience of the phase I trial and the 6-patient pilot study. The outcomes of the 6-patient pilot study suggested that multiple dosing of up to 5 separate doses was safe and well-tolerated [3]. This pilot study informed dosing for the Phase I clinical trial, which consisted of 3 doses spaced 3 months apart. The three doses were extremely well tolerated. Notably, we observed transient improvements in some patients that were not sustained after the third dose, suggesting that the peak response had not yet been reached. We propose doubling the amount of treatments and increasing the frequency to every 2 months as a way of reaching a plateau of response in patients. The peak of response needs to be established in the Phase II study.

2. Clinical Study Objectives:

2.1 Primary objective:

- To determine efficacy of multiple (6) intrathecal administrations of autologous MSC-NPs compared to placebo through assessment of disability outcomes.

2.2 Secondary objectives:

- To determine continued safety and tolerability of multiple intrathecal injections of MSC-NPs in patients with MS.

3. Study Design:

The study is a Phase II, double-blind, placebo-controlled, randomized, parallel study design with a compassionate crossover element. The IT-MSC-NP treatments and all clinical assessments will take place at a single center (Tisch MSRCNY). Both the patient and the examining neurologist will be blinded to the treatment. The treating clinician ([name], principal investigator) and the cell manufacturing coordinator ([name], co-PI) will not be blinded. Study subjects will be assigned to blocks stratified by baseline EDSS score (3.0-4.0, 4.5-5.5, 6.0, and 6.5) and disease subtype (SPMS or PPMS). The total number of subjects in each block is shown below. Subjects in each block will be randomized into placebo or treatment group in order of date of consent based on randomization scheme designated by [name]

[figure not shown]
[name] (Professor of Healthcare Policy & Research and Professor of Epidemiology in Medicine at Weill Cornell Medicine). In the second year, treated subjects will cross over to the placebo group and placebo subjects will cross over to the treated group. Study subjects are randomized in an equal fashion to study treatment and placebo at initial randomization.

Stratified block randomization scheme for Phase II trial:

| EDSS | SPMS | PPMS |
|-----------------------------|-----------|-----------|
| 3.0-4.0 | 10 | 4 |
| 4.5-5.5 | 10 | 2 |
| 6.0 | 10 | 2 |
| 6.5 | 10 | 2 |
| Total # of patients: | 40 | 10 |

The total study duration will be 3 years upon enrollment. Each study subject will be required to attend up to 18 study visits, including 1 screening visit, 1 bone marrow visit, 1 baseline visit, followed by study visits every 2 months during the treatment period of two years (12 treatment/LP procedure visits and 2 outcome visits), and an additional follow-up visit at the end of year 3.

3.1 Study design schematic

3.2 Allocation to treatment

A total of 50 study subjects will be enrolled according to inclusion/exclusion criteria. Subjects will be randomly assigned to placebo or treatment group according to the stratified block randomization scheme described above in section 3. A master randomization assignment list will be generated and kept in a locked secure location accessible only by PI ([name]) and co-PI ([name]), who are the only two un-blinded investigators in the study. [name] will remain un-blinded in order to coordinate autologous cell manufacturing for subjects in the treatment group. The PI will be responsible for maintaining the blind.

3.3 Breaking the blind

In the event of any serious adverse effects that are deemed to be a direct result of the treatment, the examining neurologist or DSMB may request for the patient to be un-blinded.

4. Subject Selection:

Fifty subjects for this study will be selected based upon their clinical disease status. Only patients with primary progressive or secondary progressive MS who have significant disability (EDSS between 3.0 and 6.5) that was not acquired within the last 12 months will be eligible. Patients should have a relatively stable disease state (duration of MS \leq 20 years at time of screening), which will allow better discernment between natural disease progression and treatment-related events. Disease stability will be determined by less than a 1.0-point change in EDSS in the last 12 months, and lack of gadolinium-enhancing lesions on an MRI and by a stable MRI disease burden (number and size of T2 lesions) in the last six months.

Enrollment criteria will also include specific clinical phenotypes which showed preliminary evidence of improvement during Phase I testing. Patients with symptomatic evidence of bladder dysfunction will be enrolled, and urodynamics testing will be conducted before and after treatment.

Exclusion criteria includes patients who have taken systemic chemotherapeutic or anti-mitotic agents within three months of the study start date due to possibility of interference with the bone marrow procedure and the potential negative impact on MSC-NP viability. Because of the experimental nature of this treatment, we are excluding patients who may be at greater risk for complications. Patients with central nervous system infections and blood diseases are at particular risk due to the route of administration of cells and the invasive nature of bone marrow aspiration. Patients who are anticipated to have difficulty accessing the intrathecal space related to scoliosis, obesity, or any other relevant factors determined by the PI. Participation in the trial will be terminated if a subject meets any of the exclusion criteria during the

course of the study. Detailed description of inclusion/exclusion criteria for this study will be provided in the clinical protocol.

Based on the close collaboration between Tisch MSRCNY and IMSMP, we do not anticipate difficulty in patient recruitment. Enrollment criteria include patients either within the geographical area or who are able to arrange reliable travel during the study period. To be enrolled, patients must consent to participate in all study visits, which include MRI. Enrollment into the study is defined as providing informed consent for study participation.

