4.2 Subject exclusion criteria

Any of the following criteria exclude a subject from this study.

- EDSS > 6.5
- Duration of disease > 20 years at time of screening (duration of disease will be determined by onset of symptoms when symptom onset is clearly defined. In cases where symptom onset is difficult to determine, duration of disease will be based on date of diagnosis).
- Change of disease modifying agent < 12 months prior to beginning treatment. Additionally, no changes in disease modifying agent will be made during the course of the study.
- Change in MS symptom management treatments, including Ampyra (dalfampridine) < 6 months prior to beginning treatment. Additionally, no changes in MS symptom management treatments will be made during the course of the study, unless there has been clinical improvement, in which case, a patient may discontinue a medication

- Start of any new orthotic device or durable medical equipment <6 months prior to beginning treatment or during the course of the study (patients may discontinue use of these devices during the course of the study if they show clinical improvement).
- All patients who have ever been on Lemtrada (alemtuzumab)
- All patients who have had any prior stem cell treatments in the past five years
- All patients who have had any prior HSCT treatments
- Pregnant or nursing mothers or any woman intending to become pregnant in the next three years
- All patients will have screening blood tests done. Only patients whose values are in the normal range as determined by the laboratory norms based on age and sex will be allowed to participate. Exceptions may be made for borderline normal laboratory values manifesting no clinical symptoms at the discretion of the Principal Investigator.
- Use of systemic chemotherapeutic or anti-mitotic medications within three months of study start date due to the possibility of interference with bone marrow procedure
- Any patients with a history of or with active malignancy
- Use of steroids within three months of the study start date, as this would suggest an active disease state
- History of cirrhosis due to increased risk of CNS infection
- Significantly uncontrolled hypertension because of increased risk for stroke or CNS hemorrhage.
- Patients with active thyroid disease resulting in hyperthyroidism or hypothyroidism (Only well controlled patients with labs in the normal range will be included) because of hormone influence on cell growth

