- Subjects will be told that their participation is voluntary and that their regular MS treatment will continue whether or not they enter the study. Consent for participation in the study will be obtained by any of the examining neurologists, the clinical trials manager, or by one of the study nurses, and documented in the subject's study file during the initial screening visit. An explanation and justification for the study will be given to the participant at this time. Consenting will occur after having had ample time to read the ICF, speak to family and friends, and review the consent with and ask questions of the consenting neurologist or study nurse. Patients will be given a copy for their records.
- Subjects will then undergo the following examinations to confirm eligibility for study participation
 - Complete physical examination with vital signs
 - Complete neurological examination
 - EDSS
 - Infectious Disease Questionnaire
 - Pregnancy test (for female patients of child-bearing age)
 - Infectious disease testing including HIV Test
 - Urine tests for drug/nicotine abuse (In addition to the screening period, a drug/nicotine urine test could be done at any time during the study for random testing)
- The EDSS evaluations will be done by the examining neurologists at Tisch MSRCNY. Every attempt will be made to have the same examining neurologist for each patient for the study duration. Examining neurologists will perform objective physical and neurological examinations during the study to evaluate efficacy, and will be blinded to the treatment
- All patients will be required to go to a clinical laboratory facility to undergo a panel of infectious disease screening. The results will be sent to the screening neurologist, and any patient positive for any infectious diseases will be excluded from the study.
- Screening Blood Draw
- The initial screening will last 1 hour.

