6.2 Study drug procedures

Bone Marrow Visit (Month -3):

- This visit will occur approximately one month after enrollment and approximately 3 months prior to the first treatment.
- Vital signs will be documented
- A bone marrow aspiration will be performed by [name], an experienced, board certified hematologist affiliated with the Tisch MSRCNY. [name] will obtain a bone marrow aspirate from the sternum or the iliac crest under sterile conditions following standard procedure. An adult bone marrow kit with a heparinized syringe will be used.

- Bone marrow aspirate will be obtained from the manubrium of the sternum, at the level of the second intercostal space. Alternatively, aspirate may be obtained from the iliac crest. Bone marrow will be aspirated using an adult bone marrow kit with a heparinized syringe.
- Each research subject's sterile bone marrow sample will be placed in a pre-labeled bag and immediately transferred from the clinic to the stem cell culture laboratory. Patients will be told not to shower or get their bandage wet for 24 hours following the procedure. In order for patients to move to the next phase of the study, their cells must be viable and pass bone marrow release testing. If for some reason cells do not thrive, the patient's involvement in the study will be reevaluated.
- Total duration of the Bone Marrow Visit is approximately 2 hours and will be conducted at the Tisch MSRCNY due to necessary proximity to the cell manufacturing laboratory.
- Cells from subjects who have had bone marrow harvested under the long-term ongoing research protocol, "Harvesting Bone Marrow for Neural Stem Cells" (Former St. Luke's-Roosevelt IRB# 08-049) (Current WIRB# 20162012), can be used for implantation as long they are deemed acceptable for use (and eliminate any risk from an unnecessary marrow harvesting procedure). This includes bone marrow harvested under this long-term ongoing research protocol harvested prior to enrollment in this study.

Baseline Visit (Month-1; within one month prior to first treatment):

- The purpose of the baseline visit is to establish baseline values of outcome assessments prior to treatment.
- The following baseline visit exams will be conducted by study subject's examining neurologist and study coordinator (duration approximate 1 hour)
 - Vital signs-Only if not performed at screening
 - Physical exam-Only if not performed at screening
 - Neurological exam-Only if not performed at screening
 - Headache pain scale

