## 1.5 Sample Size and Randomization

A total of 50 study subjects will be enrolled based on power analysis based on 20 participants in each group of the Phase II study. Group sample size of 20 in the treatment group and 20 in the placebo group achieve more than 80% power to detect a difference between the group proportions of 35%, using a two-sided Z-test with pooled variance and using a significance level of 0.05. This calculation assumes that 40% of patients in the treatment group and 5% of patients in the placebo group achieve at least one of the EDSS-Plus components. The prevalence of patients with improved outcome is informed by the results of our Phase I trial, in which 40% of patients experienced a decrease of 0.5 or more on EDSS. A total of 50 patients (25 patients in each group) will initially be enrolled to account for an expected attrition rate of 20%.

Subjects will be stratified according to baseline EDSS score (3.0-4.0, 4.5-5.5, 6.0, and 6.5) and disease subtype (SPMS or PPMS), and block randomized within each stratum. The total number of subjects to be enrolled in each subgroup is shown below. Subjects are stratified and block randomized into placebo or treatment group in order of date of enrollment based on randomization scheme designated by [name]. Study subjects are randomized in an equal fashion to study treatment and placebo at initial randomization.

EDSS	SPMS	PPMS
3.0-4.0	10	4
4.5-5.5	10	2
6.0	10	2
6.5	10	2
Total # of patients:	40	10

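### Allocation follows consent order, eligibility need not be final first, and the unblinded PI who holds the list decides discretionary exclusions, so allocation can be known before eligibility is settled.

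*Protocol*

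**What the plan says.** **Meaning of enrolment.** Protocol section 4 (Subject Selection) says: "Enrollment into the study is defined as providing informed consent for study participation". Section 3.2, however, has the 50 subjects enrolled in line with the inclusion and exclusion criteria, and section 4.1 makes the inclusion criteria a requirement for enrolment.

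**Order of allocation.** Protocol section 3: "Subjects in each block will be randomized into placebo or treatment group in order of date of consent". SAP 1.5: "Subjects are stratified and block randomized into placebo or treatment group in order of date of enrollment". The strata need a score: "Study subjects will be assigned to blocks stratified by baseline EDSS score", crossed with SPMS/PPMS.

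**What comes after consent.** Protocol section 6.1, following the consent step: "Subjects will then undergo the following examinations to confirm eligibility for study participation". These include the EDSS, infectious disease, pregnancy and drug/nicotine tests; a screening blood draw is also taken. Section 6.2 puts the marrow visit about one month after enrolment and about three months before first treatment, and adds: "In order for patients to move to the next phase of the study, their cells must be viable and pass bone marrow release testing". If cells do not thrive, the patient's involvement is only to be re-evaluated.

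**Who holds the list and who decides.** The master list is "kept in a locked secure location accessible only by PI" and the co-PI, the two unblinded investigators (section 3.2). Under section 4.2, on laboratory values: "Exceptions may be made for borderline normal laboratory values manifesting no clinical symptoms at the discretion of the Principal Investigator". The same section leaves other major disease and difficulty of intrathecal access to the PI's judgement.

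**Sample size and analysis set.** Protocol 9.2 and SAP 1.5 plan 20 per arm, raised to 25 per arm (50 in total) for 20% attrition. SAP 4.1 limits the primary analysis to subjects who meet the criteria and complete year 1 and its three-month assessment.

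**The concern.** Allocation concealment requires that whoever decides a subject's eligibility cannot know the arm at that time. Here one person has the list and exercises the discretion, and the queue position is fixed at consent, before the checks. If a borderline case is judged differently according to the arm coming next, the groups are no longer comparable. The primary analysis would not show it, because subjects ruled ineligible are outside the analysis set.

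A second consequence concerns numbers. If the 50 counts consents, losses at screening and marrow release may come from the same 50 that were sized only for 20% attrition.

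**Working it through.** **1. Can the allocation be known before eligibility is final?**

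| Step | Source | Fixed at that point |
|---|---|---|
| Consent (= enrolment in section 4) | Protocol 4, 6.1 | Date that sets the queue |
| EDSS at screening | Protocol 6.1 | Stratum, hence position in the stratum |
| Laboratory, infection and other checks; PI discretion | Protocol 6.1, 4.2 | Eligibility |
| Marrow release | Protocol 6.2 | Whether the patient can proceed |
| First treatment | Protocol 6.2 | – |

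Consent date plus EDSS band plus subtype gives a position in the stratum, and the list turns that position into an arm. Someone with the list can do this once the EDSS is known, whenever the code is formally issued. No section requires the third and fourth steps to be finished first. The rules as written therefore allow the arm to be known before eligibility is decided.

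**2. The plan's own figures.** Inputs from Protocol 9.2: 40% versus 5%, 20 per arm, two-sided pooled Z-test, alpha 0.05, attrition 20%.

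- Inflation: 20 / (1 − 0.20) = 25 per arm, 50 in total. This reproduces the plan and is fully used by the 20% attrition.
- Exact power: sum Bin(a; n, 0.40) × Bin(b; n, 0.05) over all pairs (a, b) for which the test rejects, where z = (a/n − b/n) / √(2p̄(1 − p̄)/n) and p̄ = (a + b)/(2n). At n = 20 this gives 82.0%, which agrees with the stated power of more than 80%. The pooled normal approximation gives 77.7%.
- Fisher's exact test, which the analysis plan also allows, has 71.6% power at n = 20.

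**3. If pre-treatment losses come out of the 50.** The documents give no screening or marrow failure rate, so the loss s is an assumption. Evaluable subjects per arm = 50 × (1 − s) × 0.80 / 2.

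| Assumed s | Evaluable per arm | Exact Z-test power | Fisher power |
|---|---|---|---|
| 0% | 20 | 82.0% | 71.6% |
| 10% | 18 | 76.9% | 64.7% |
| 20% | 16 | 73.5% | 56.5% |

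Each column should be read against its own first row. The difference between 82.0% and 71.6% comes from the choice of test and has nothing to do with enrolment. At 19 per arm the exact Z-test power is 79.6%, so one evaluable subject fewer per arm already takes it below 80%.

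**4. Consents needed for 50 randomised subjects.** 50 / 0.90 = 55.6, so 56. 50 / 0.80 = 62.5, so 63. That is 6 to 13 more than 50.

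**The case against.** A reader might infer that eligibility is in fact settled after allocation, and that failures in fact use up randomised slots. The documents do not support either as fact.

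- Consent order is a ranking rule; no section dates the act of randomisation. Assignment at consent is not workable, because the EDSS stratum is scored afterwards. The list could be applied after screening and marrow release and still follow consent order.
- Protocol 3.2 and 4.1 make the criteria a condition of enrolment, and the table in section 3 places all 50 in EDSS-by-subtype cells, which fits classified subjects better than unscreened consents.
- Reuse of slots was contemplated. Section 5.1.1 passes a non-compliant subject's allocation to a new subject. Section 8.4 replaces subjects discontinued during treatment, while section 13.1 does not; the two must be reconciled, and neither clearly covers failure before treatment.
- Attrition is not defined. If the 20% already covers pre-treatment loss, the shortfall disappears. In the Phase I trial, as the Protocol reports it, 20 were enrolled and all 20 received all three treatments.
- The route to bias is narrow. Infection results go to the screening neurologist and positives are excluded by rule. The marrow gate applies to patients generally, and both arms are due cells in one of the two years, so marrow failure need not differ by arm.

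All of this stands, and it makes the power figures conditional. It does not remove the concealment problem, which rests on the PI's discretion combined with access to the list. Formal assignment after screening would not by itself restore concealment, because the list-holder could already work out the arm. The two meanings of enrolment are themselves a reason to act, since through SAP 1.5 they govern the allocation order as well as the count of 50.

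**Conclusion.** The point holds as a gap in concealment and in definition. The plan lets a subject's allocation be known to the person deciding discretionary exclusions before eligibility is final, and such exclusions leave the primary analysis. The documents do not show that this has happened, and the size of any bias cannot be computed from them.

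The power loss is conditional on three things: the 50 are consents, failures are not refilled, and the 20% excludes pre-treatment loss. If all three hold, an assumed 10–20% loss lowers exact Z-test power from 82.0% to 76.9–73.5%, and Fisher power from 71.6% to 64.7–56.5%. If any one fails, this calculation does not apply. It would be wrong to read it as showing that the trial is underpowered for this reason. The change is worth making because it is cheap and closes an avoidable route to bias.

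**What to change.** Amend Protocol sections 3, 3.2, 4 and 9.2 and SAP 1.5 so that:

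1. the next code in the stratum is assigned only after documented eligibility sign-off and marrow release, in order of that date;
2. the statistician who designates the scheme holds the list and releases each code only after sign-off. Changing the order alone is not enough, because a PI with the list can still see the next code. The co-PI can be told each assignment on release for manufacturing purposes;
3. the 50 (25 per arm) and the 20% attrition allowance apply to randomised subjects, and enrolment has one meaning throughout.

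If randomisation is already complete, report when each assignment was made relative to the eligibility decision and marrow release, and account for all consented subjects, by arm where one was assigned.

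One limit remains. Three PPMS cells hold two patients each. If each is split evenly, the unblinded PI can infer the second assignment from the first even without the list. Having someone blinded take the discretionary eligibility decisions would close this too.

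The cost is wording in the sections named, a code-release step with the statistician, and about 6 to 13 more consents at 10–20% pre-treatment loss.
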